3. OBJECTIVES

3.1. Primary objective

- To assess the immunological response to hepatitis B antigen, in terms of antibody concentrations ≥ 100 mIU/ml, one month after the single challenge dose of the HBV vaccine in subjects 14-15 years of age, previously vaccinated with four doses of Infanrix hexa in the first two years of life.

3.2. Secondary objectives

- To assess the persistence of anti-HBs antibodies, in terms of seroprotection status and antibody concentrations, in subjects 14-15 years of age, previously vaccinated with four doses of Infanrix hexa in the first two years of life.
- To assess the immunological response to hepatitis B antigen, in terms of anamnestic response, one month after the single challenge dose of the HBV vaccine in subjects 14-15 years of age, previously vaccinated with four doses of Infanrix hexa in the first two years of life.
- To assess the immunological response to the hepatitis B antigen, in terms of seroprotection status and antibody concentrations, one month after the single challenge dose of the HBV vaccine in subjects 14-15 years of age, previously vaccinated with four doses of Infanrix hexa in the first two years of life.
- To evaluate the safety and reactogenicity of a single challenge dose of HBV vaccine (Engerix-B Kinder) in terms of solicited symptoms (local and general), unsolicited symptoms and serious adverse events (SAEs).

4. ENDPOINTS

4.1. Primary endpoint

- Immunogenicity to components of the study vaccine.
 - Anti-HBs antibody concentrations ≥ 100 mIU/ml, one month after the single challenge dose of HBV vaccine.

4.2. Secondary endpoints

- Anti-HBs antibody persistence after previous vaccination with *Infanrix hexa*.
 - Anti-HBs antibody concentrations ≥ 10 mIU/ml, ≥ 100 mIU/ml and anti-HBs antibody concentrations before the single challenge dose of HBV vaccine.
- Immunogenicity to the components of the study vaccine.
 - Anti-HBs antibody concentrations ≥ 10 mIU/ml and anti-HBs antibody concentrations one month after the single challenge dose of HBV vaccine.
 - Anamnestic response to the single challenge dose of HBV vaccines.
- Solicited local and general symptoms.
 - Occurrence of each solicited local and general symptom during the 4-day (Day 0–3) follow-up period after the single challenge dose of HBV vaccine.
- Unsolicited adverse event
 - Occurrence of unsolicited AEs during the 31-day (Day 0–30) follow-up period after the single challenge dose of HBV vaccine.
- Serious adverse event
 - Occurrence of serious adverse events after the single challenge dose of HBV vaccine up to study end.

5. ANALYSIS SETS

5.1. Definition

Three cohorts are defined for the purpose of analyses:

- Total vaccinated cohort (TVC)
- According To Protocol (ATP) cohort for analyses of Immunogenicity

5.1.1. Total vaccinated cohort

The TVC will include all subjects who received the single challenge dose of HBV vaccine.

- The TVC for the analyses of safety will include all subjects with study vaccine administration documented.
- The TVC for the analyses of immunogenicity will include all subjects who have received a single challenge dose of HBV vaccine and for whom data concerning immunogenicity endpoint measures are available.

5.1.2. According-to-protocol cohort for analyses of immunogenicity

The ATP cohort for analysis of immunogenicity will include all subjects who satisfy the below criteria:

- who meet all eligibility criteria
- who comply with the procedures and intervals defined in the protocol.
- who do not meet any of the elimination criteria during the study
- for whom post-vaccination immunogenicity (Visit 2) results are available.

The interval between vaccination at Visit 1 and blood sampling at Visit 2, considered for inclusion of a subject in the ATP cohort for analyses of immunogenicity will be 21-48 days.

5.2. Criteria for eliminating data from Analysis Sets

Elimination codes are used to identify subjects to be eliminated from analysis. Detail is provided below for each set below.

5.2.1. Elimination from Total Vaccinated Cohort

Code 1030 (Study vaccine not administered at all) and code 900 (invalid informed consent or fraud data) will be used for identifying subjects eliminated from TVC.

5.2.2. Elimination from ATP cohort for analyses of Immunogenicity

5.2.2.1. Excluded subjects

A subject will be excluded from the ATP analysis under the following conditions

Code	Condition under which the code is used
900	Invalid informed consent or fraud data
1030	Study vaccine not administered at all
1040	Administration of concomitant vaccine(s) forbidden in the protocol
1070	Administration not according to protocol for reason specified by the investigator, other than side, site and route.
1080	Vaccine has been administered (effective treatment number) despite a temperature deviation qualified by Status QA GMP NON Use.
1090	Vaccine has been administered (effective treatment number) out of the expiration date at the time of administration.
2010	Protocol violation linked to the inclusion/exclusion criteria including age.
2040	Administration of any concomitant medication forbidden by the protocol.
2050	Underlying medical condition identified after dose 1 and forbidden by the protocol.
2060	Concomitant infection after dose 1 which is related to the vaccine which may influence immune response ie Subjects with evidence of hepatitis B infection or disease as identified by anti-HBc at visit 2
2070	Concomitant infection after dose 1 which is not related to the vaccine which may influence immune response (e.g. Hepatitis infection in a lyme study)
2090	Blood sample taken but: non compliance with blood sampling schedules (dates of BS not corresponding to adapted protocol intervals or unknown BS/vaccination dates) blood sample should be taken within 21-48 days post dose 1.
2100	Serological results not available for all antigens (ie anti-HBs and anti-HBc) POST vaccination (including lost samples, blood sample not done, unable to test, and absence of parallelism).
2120	Obvious incoherence, abnormal serology evolution or error in data (incoherence between CRF and results, wrong sample labelling)

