5.6.10. Study Vaccine administration

- After completing all prerequisite procedures prior to vaccination, one dose of study vaccine will be administered intramuscularly (IM) in the deltoid region of the non-dominant arm (refer to Section 6.3 for detailed description of the vaccine administration procedure). If the investigator or delegate determines that the subject's health on the day of administration temporarily precludes vaccine administration, the visit will be rescheduled within the allowed interval for this visit (see [Table 5](#))
- The subjects will be observed closely for at least 30 minutes following the administration of the vaccine, with appropriate medical treatment readily available in case of anaphylaxis.

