6.3. Dosage and administration of study vaccine

All subjects will receive one dose of the HBV vaccine. The vaccine will be administered as an IM injection at a 90-degree angle into the deltoid region of the non-dominant arm (preferably). In order to ensure proper IM injection of the study vaccine, a needle of at least 1 inch (2.54 cm) length, 25 gauge will be used [CDC, 2002].

The dosage and administration of study vaccines is presented in [Table 10](#).

Table 10 Dosage and administration

Type of contact and timepoint	Volume to be administered	Treatment name	Route ¹	Site	Side
Visit 1 (Day 0)	0.5 ml	HBV	IM	Deltoid region of arm	Preferably Non-dominant

¹IM: Intramuscular

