6.6. Warnings and precautions

- *Engerix-B Kinder* should not be administered in the buttock or intradermally since this may result in lower immune response.
- *Engerix-B Kinder* should under no circumstances be administered intravenously.
- Syncope (fainting) can occur following, or even before any vaccination especially in adolescents as a psychogenic response to the needle injection. It is important that procedures are in place to avoid injury from syncope.
- Due to the long incubation period of hepatitis B, it is possible for unrecognised infection to be present at the time of vaccination. The vaccine may not prevent hepatitis B in such cases.

Refer to the approved product label/package insert.

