5.3. Important protocol deviation not leading to elimination from ATP cohort

The following important protocol deviations will be reported:

- In case of unexpected vaccinations at study start was granted due to regulatory recommendation, the subjects who had such vaccination could be mentioned.
- Subjects attending visit 2 alone without parents being present.
- Protocol deviations related to informed consent and not leading to eliminations.

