9. CHANGES FROM PLANNED ANALYSES

The major changes from the protocol are,

- According-to-protocol cohort for analyses of antibody persistence defined in the protocol for the analysis of antibody persistence was removed from the SAP to reduce the number of cohorts used in the analysis. The analysis of persistence and response to challenge dose will be performed on the According-to-protocol cohort for analyses of immunogenicity. This change will not have significant impact on the analysis of persistence as no major difference in number of subjects expected between the ATP cohort for analysis of Immunogenicity and ATP cohort for analyses of antibody persistence.

Other changes include,

- The analysis for persistence and response to challenge dose is harmonized with respect to the cut-offs to consider.
 - The analysis to summarize the number and percentage of subjects between >10 mIU/mL and < 100 mIU/mL planned in the protocol was removed to be consistent with the endpoints of the study.
 - The analysis to summarize the post challenge dose response and anamnestic response stratified by the pre-challenge dose concentrations will be performed by considering the categories < 6.2 mIU/ml, ≥ 6.2 mIU/ml - < 10 mIU/ml, and ≥ 10 mIU/ml at pre-challenge dose time point.
- All the analysis of solicited and/or unsolicited adverse events will be performed for any, grade 3, by relationship to vaccination, and requiring medical attention to be consistent with the presentation of the adverse events summary.

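### SAP elimination code 1070 exempts wrong injection site and route, and no other code covers them, so the code list keeps subjects whom the ATP immunogenicity cohort definition excludes

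*SAP*

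**What the plan says.** **Cohort definition.** SAP 5.1.2 and protocol 10.4.2 give the same four conditions for the ATP cohort for immunogenicity. One is that it contains subjects "who comply with the procedures and intervals defined in the protocol". Meeting none of the elimination criteria is a separate condition. SAP 6.3.1 bases the primary analyses on this cohort.

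**Elimination codes.** SAP 5.2 states: "Elimination codes are used to identify subjects to be eliminated from analysis". In SAP 5.2.2.1, code 1070 is worded "Administration not according to protocol for reason specified by the investigator, other than side, site and route".

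**Administration procedure.** Protocol 6.3 has the vaccine "administered as an IM injection at a 90-degree angle into the deltoid region of the non-dominant arm (preferably"), and Table 10 repeats this. In both places the qualifier applies to the side only.

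**Relevance to the endpoint.** Protocol 6.6 says that the vaccine "should not be administered in the buttock or intradermally since this may result in lower immune response".

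**Status of the analyses.** SAP section 7 describes all analyses as descriptive.

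**The concern.** Route and site are procedures that the protocol fixes, so a departure from either breaks the compliance condition. The code list is the tool for applying that condition, yet it exempts both. An analyst who builds the cohort from the codes keeps such a subject. One who builds it from the definition drops the subject.

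What is at stake is the composition of the primary analysis set, and through it the percentage with anti-HBs of at least 100 mIU/ml and its confidence interval. The exemption includes two kinds of administration that the protocol itself links to a possibly weaker response. Keeping those subjects would tend to lower the estimate.

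**Working it through.** **1. Does any other code catch a wrong site or route?** SAP 5.2.2.1 has 14 codes. Apart from 1070 they cover:

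| Codes | Subject |
|---|---|
| 900, 1030 | invalid consent or fraud; vaccine not given |
| 1040, 2040 | forbidden vaccine; forbidden medication |
| 1080, 1090 | temperature deviation; expired vaccine |
| 2010 | eligibility, including age |
| 2050, 2060, 2070 | medical condition; infections |
| 2090, 2100, 2120 | sampling dates; missing serology; incoherent data |

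None covers site or route. Annex 2 of the SAP only refers back to section 5.2.

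**2. The passages applied to one case.** Take an intradermal dose in an otherwise compliant subject with a Visit 2 result.

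- Compliance condition (SAP 5.1.2, protocol 10.4.2, read with protocol 6.3): not met, so out.
- Elimination codes (SAP 5.2.2.1): none assigned, so in.

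A wrong side alone gives no such conflict, because protocol 6.3 and Table 10 make the side a preference.

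**3. Does the second analysis resolve it?** The complementary TVC analysis in SAP 6.3.1 runs only if 5% or more of vaccinated subjects with serology are excluded from the ATP cohort. Subjects kept by the exemption do not count towards that 5%, and the TVC contains them anyway. It cannot show the effect of removing them.

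**4. The plan's own figure.** Protocol 10.3 states at least 86% power with 270 evaluable subjects and a true response of 95%, for a 95% lower limit above 90%. By the exact one-sided binomial test at 0.025, the smallest qualifying count is 253 of 270:

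- P(X ≥ 253 | 270, 0.90) = 0.0218
- power = P(X ≥ 253 | 270, 0.95) = 86.7%

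The stated power reproduces, and this point does not alter it.

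**5. Size, on assumed counts.** The documents give neither a frequency of site or route deviations nor a response rate after them. Assume that 1 to 5 of the 270 have one. The base is 0.95 × 270 = 256.5, taken as 257 responders and 13 non-responders. Intervals are Clopper-Pearson, as in the SAP. The shift is the estimate after removal minus the base estimate.

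| Removed | Of these, non-responders | Result | 95% CI | Shift (points) |
|---|---|---|---|---|
| 0 | – | 257/270 = 95.19% | 91.91 to 97.41 | – |
| 1 | 1 | 257/269 = 95.54% | 92.34 to 97.67 | +0.35 |
| 3 | 3 | 257/267 = 96.25% | 93.22 to 98.19 | +1.07 |
| 5 | 5 | 257/265 = 96.98% | 94.14 to 98.69 | +1.80 |
| 5 | 2 | 254/265 = 95.85% | 92.69 to 97.91 | +0.66 |
| 5 | 0 | 252/265 = 95.09% | 91.76 to 97.36 | −0.09 |

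The +1.80 is the largest shift for five subjects. It requires all five to be among the 13 non-responders. If these subjects respond like the others, the shift is about 0.

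**The case against.** The best defence is that the specific rule applies the general one. The compliance condition is generic and does not say which departures cost membership. The codes do, and code 1070 addresses site and route expressly. The protocol's own passages on ATP elimination (the Table 5 footnote, 5.7.1, 6.7.2 and 6.8) do not name site or route either. An analyst who follows SAP 5.2 therefore gets one answer: keep the subject.

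That shows what the codes do, but it does not remove the conflict. SAP 5.1.2 makes compliance a condition of its own, in addition to the absence of elimination criteria. A subject without a code has met the second condition, not the first.

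Three other arguments for the plan stand:

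- **Side.** A reader might infer that the protocol contradicts itself, because 5.6.10 has the vaccine "administered intramuscularly (IM) in the deltoid region of the non-dominant arm" with no qualifier. The same sentence refers to 6.3 for the detailed procedure, and 6.3 makes the side a preference. There is no conflict to reconcile.
- **Disclosure.** A reader might infer that the exemption is concealed, because it is absent from SAP 5.3 ("Important protocol deviation not leading to elimination from ATP cohort") and from section 9. It is printed in the operative elimination table. SAP 5.3 concerns important deviations, and section 9 opens with "The major changes from the protocol are" and then introduces its remaining items in terms that do not claim completeness. The documents do not support concealment.
- **Impact.** Every count in the illustration is assumed. Protocol 6.6 says only that the response may be lower, names buttock and intradermal administration only, and gives no size. Keeping weaker responders is also conservative for a response rate.

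**Conclusion.** The mismatch is real and confined to site and route. Applied as written, the codes keep in the primary cohort subjects who do not meet its definition, including those given the vaccine in ways that the protocol says may weaken the response.

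The consequence is minor. On 1 to 5 assumed subjects, the descriptive estimate moves by between about 0 and 1.8 points. The top of that range needs five deviations, all in non-responders, and nothing in the documents makes that likely or unlikely.

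A reader might infer that the primary conclusion or the 86% power is compromised. The documents do not support that. There is one group, the objectives are descriptive, the 90% lower limit is used only to justify the sample size, and no deviation rate is given from which a loss could be derived.

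**What to change.** Limit the exemption in code 1070 to side, so that departures from the site and route in protocol 6.3 and Table 10 lead to elimination from the ATP cohort for immunogenicity, as SAP 5.1.2 already requires.

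If the sponsor intends the wider exemption, say so in SAP 5.1.2, so that the definition and the codes agree, and list it in section 9.

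Either way the cost is a change of SAP wording, with no new data and no additional analysis. The side wording in protocol 5.6.10 needs no change.

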5.2.2.2. Right censored Data

NA

5.2.2.3. Visit-specific censored Data

NA

5.3. Important protocol deviation not leading to elimination from ATP cohort

The following important protocol deviations will be reported:

- In case of unexpected vaccinations at study start was granted due to regulatory recommendation, the subjects who had such vaccination could be mentioned.
- Subjects attending visit 2 alone without parents being present.
- Protocol deviations related to informed consent and not leading to eliminations.

6. STATISTICAL ANALYSES

Note that standard data derivation rule and stat methods are described in annex 1 and will not be repeated below. All Confidence Interval (CI) will be two-sided 95% CI.

6.1. Demography

6.1.1. Analysis of demographics/baseline characteristics planned in the protocol

The following calculations will be performed:

- The distribution of subjects enrolled among the study centres will be tabulated.
- The numbers of subjects who withdraw from the study will be tabulated according to the reason for drop-out.
- The deviations from specifications for age and intervals between study visits will be tabulated.
- The median, mean, range and standard deviation of age (in years) at the Visit 1. The median, mean and standard deviation of height (in centimeters), weight (in kilograms) and BMI (in kilograms per meter square) at Visit 1 will be computed. The racial and sex composition will be presented.
- Number and reason for elimination from ATP cohort will be tabulated.

6.1.2. Additional considerations

All demography summaries will be generated for the TVC. The summary of age, height, weight, BMI, race and sex composition will also be provided for the ATP cohort for Immunogenicity.

6.2. Exposure

6.2.1. Analysis of exposure planned in the protocol

NA

6.2.2. Additional considerations

The number of subjects who received the challenge dose will be tabulated.

6.3. Immunogenicity

6.3.1. Analyses for antibody persistence and response to challenge dose

The primary analyses will be based on the ATP cohort for analyses of immunogenicity. If, the percentage of vaccinated subjects with serological results excluded from the ATP cohort for analyses of immunogenicity is 5% or more, a second analyses based on the TVC will be performed to complement the ATP analyses.

- Prior to the single dose of HBV vaccine and one month after the single challenge dose of HBV vaccine:
 - Percentage of subjects with anti-HBs antibody concentrations ≥ 6.2 mIU/ml (seropositive), ≥ 10 mIU/ml and ≥ 100 mIU/ml, with exact 95% CI will be calculated [Clopper, 1934].
 - GMCs with 95% CI will be calculated for anti-HBs antibodies.
 - The distribution of anti-HBs antibody concentrations will be displayed using RCCs.
- The percentage of subjects with anti-HBs concentrations ≥ 6.2 mIU/ml, ≥ 10 mIU/ml, and ≥ 100 mIU/ml (with exact 95% CI [Clopper, 1934]) and GMCs at the post-HBV challenge dose time-point, in relation to their pre-challenge dose status (< 6.2 mIU/ml, ≥ 6.2 mIU/ml - < 10 mIU/ml, ≥ 10 mIU/ml) will be tabulated.
- Percentage of subjects (with 95% CI [Clopper, 1934]) who mount an anamnestic response to the single challenge dose of HBV vaccine will be calculated overall and in relation to their pre-vaccination status (< 6.2 mIU/ml, ≥ 6.2 mIU/ml - < 10 mIU/ml, ≥ 10 mIU/ml).
- Post-challenge anti-HBs antibody concentrations as a function of pre-challenge concentrations, with regression line will be computed using linear regression method for ATP cohort for immunogenicity. The model will include pre-challenge log transformed concentrations as regressor (independent or explanatory variable) and post-challenge log-transformed concentrations as an outcome (dependent or response) variable. Antibody concentrations observed at the pre-challenge dose time point will be presented graphically.

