10.7. Analyses of immunogenicity

Analyses for antibody persistence

The analyses for antibody persistence will be performed on the ATP cohort for analyses of antibody persistence.

- Prior to the single dose of HBV vaccine:
 - Percentage of subjects with anti-HBs antibody concentrations ≥ 6.2 mIU/ml, ≥ 10 mIU/ml, ≥ 10 mIU/ml to < 100 mIU/ml, and ≥ 100 mIU/ml, with exact 95% CI will be calculated [[Clopper](#), 1934].
 - GMCs with 95% CI will be calculated for anti-HBs antibodies.
 - The distribution of anti-HBs antibody concentrations will be displayed using reverse cumulative curves (RCCs).

Response to challenge dose

The primary analyses will be based on the ATP cohort for analyses of immunogenicity. If, the percentage of vaccinated subjects with serological results excluded from the ATP cohort for analyses of immunogenicity is 5% or more, a second analyses based on the TVC will be performed to complement the ATP analyses.

- One month after the single challenge dose of HBV vaccine:
 - Percentage of subjects with anti-HBs antibody concentrations ≥ 6.2 mIU/ml, ≥ 10 mIU/ml and ≥ 100 mIU/ml, with exact 95% CI will be calculated [Clopper, 1934].
 - GMCs with 95% CI will be calculated for anti-HBs antibodies.
 - The distribution of anti-HBs antibody concentrations will be displayed using RCCs.
- The percentage of subjects with anti-HBs concentrations ≥ 6.2 mIU/ml, ≥ 10 mIU/ml, and ≥ 100 mIU/ml (with exact 95% CI) and GMCs at the post-HBV challenge dose time-point, in relation to their pre-challenge dose status (< 6.2 mIU/ml, < 10 mIU/ml, ≥ 10 mIU/ml) will be tabulated [Clopper, 1934].
- Percentage of subjects (with 95% CI) who mount an anamnestic response to the single challenge dose of HBV vaccine will be calculated overall and in relation to their pre-vaccination status (< 6.2 mIU/ml, < 10 mIU/ml, ≥ 10 mIU/ml) [Clopper, 1934].
- Post-challenge anti-HBs antibody concentrations as a function of pre-challenge concentrations, with regression line will be computed using linear regression method for ATP cohort for immunogenicity only. The model will include pre-challenge log transformed concentrations as regressor (independent or explanatory variable) and post-challenge log-transformed concentrations as an outcome (dependent or response) variable. Antibody concentrations observed at the pre-challenge dose time point will be presented graphically.

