7. ANALYSIS INTERPRETATION

All analyses are descriptive.

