11.2.4. Immunogenicity

- A seronegative subject is a subject with anti-HBs antibody concentration below the assay cut-off (< 6.2 mIU/ml).
- A seropositive subject is a subject with anti-HBs antibody concentrations above the assay cut-off (≥ 6.2 mIU/ml).

- A seroprotected subject is a subject with anti-HBs antibody concentrations above the protection level (≥ 10 mIU/ml).
- Anamnestic response to the single challenge dose is defined as:
 - At least (i.e. greater than or equal to) 4-fold rise in post-vaccination anti-HBs antibody concentrations in subjects seropositive at the pre-vaccination time point.
 - Post-vaccination, anti-HBs antibody concentrations ≥ 10 mIU/ml in subjects seronegative at the pre-vaccination time point.
- The Geometric mean antibody concentrations (GMCs) calculations will be performed by taking the anti-log of the mean of the \log_{10} concentration transformations. All subjects will be considered. Subjects whose antibody concentrations are below the cut-off of the assay will be given an arbitrary value of half the cut-off for the purpose of GMC calculation. Note that as per assay specification, results between the assay cut-off of 6.2 mIU/ml and 7.65 mIU/ml (= Lower limit of Quantification) will be quantified as 6.2 mIU/ml.
- For a given subject and a given immunogenicity measurement, missing or non-evaluable measurements will not be replaced. Therefore, an analysis will exclude subjects with missing or non-evaluable measurements.
- All CI computed will be two-sided 95% CI.

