Template 10 Reverse cumulative distribution curve of anti-HBs antibody concentrations at <pre-challenge dose/one month after the challenge dose> (ATP cohort for analysis of immunogenicity)

HBV Group= Subjects who previously received 4 doses of Infanrix hexa in first two years of life and received a challenge dose of HBV vaccine in this study

Note: The groups shown in figure are indicative only. Actual groups may differ.

Template 11 Percentage of subjects with antibody concentrations ≥ 6.2 mIU/mL, ≥ 10 mIU/mL, ≥ 100 mIU/mL and GMCs for anti-HBs antibody concentrations stratified based on the pre-challenge dose status (ATP cohort for analysis of immunogenicity)

Group	Pre-vaccination status			≥ 6.2 mIU/mL		≥ 10 mIU/mL		≥ 100 mIU/mL		GMC				
		Timing	N	n	%	95% CI		95% CI		95% CI		value	LL	UL
						LL	UL	LL	UL	LL	UL			
HBV Group	< 6.2 mIU/mL	Pre												
		P1(D30)												
	≥ 6.2 mIU/mL - <10 mIU/mL	Pre												
		P1(D30)												
	≥ 10 mIU/mL	Pre												
		P1(D30)												
	Overall	Pre												
		P1(D30)												

HBV Group= Subjects who previously received 4 doses of Infanrix hexa in first two years of life and received a challenge dose of HBV vaccine in this study

GMC = geometric mean antibody concentration calculated on all subjects

N = number of subjects with available results

n/% = number/percentage of subjects with concentration within the specified range

95% CI = 95% confidence interval; LL = Lower Limit, UL = Upper Limit

Pre: Blood sampling at pre-challenge dose time point

P1(D30): Blood sampling one month after the challenge dose

Template 12 Anamnestic response for anti-HBs antibodies at one month after the challenge dose (ATP cohort for analysis of immunogenicity)

Group	Pre-vaccination status	Anamnestic response to the challenge dose				
				95% CI		
		N	n	%	LL	UL
HBV Group	S-					
	S+					
	Total					

HBV Group= Subjects who previously received 4 doses of Infanrix hexa in first two years of life and received a challenge dose of HBV vaccine in this study

S- = seronegative subjects (antibody concentration < 6.2mIU/mL for anti-HBs) prior to vaccination

S+ = seropositive subjects (antibody concentration \geq 6.2mIU/mL for anti-HBs) prior to vaccination

Total = subjects either seropositive or seronegative at pre-vaccination Challenge Dose response is defined as:

For initially seronegative subjects, antibody concentration greater than or equal to 10mIU/mL (\geq 10mIU/mL)

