For initially seropositive subjects: antibody concentration at least four times the pre-challenge antibody concentration

N = number of subjects with both pre- and post-vaccination results available

n(%) = number(percentage) of responders

95% CI = exact 95% confidence interval; LL = lower limit, UL = upper limit

Template 13 Anamnestic response for anti-HBs antibodies at one month after the challenge dose stratified based on the pre-challenge dose status (ATP cohort for analysis of immunogenicity)

Group	Pre-vaccination status	Anamnestic response to the challenge dose				
				95% CI		
		N	n	%	LL	UL
HBV Group	< 6.2 mIU/mL					
	\geq 6.2 mIU/mL - <10 mIU/mL					
	\geq 10mIU/mL					
	Total					

HBV Group= Subjects who previously received 4 doses of Infanrix hexa in first two years of life and received a challenge dose of HBV vaccine in this study

S- = seronegative subjects (antibody concentration < 6.2mIU/mL for anti-HBs) prior to vaccination

S+ = seropositive subjects (antibody concentration \geq 6.2mIU/mL for anti-HBs) prior to vaccination

Total = subjects either seropositive or seronegative at pre-vaccination Challenge Dose response defined as:

For initially seronegative subjects, antibody concentration greater than or equal 10mIU/mL (\geq 10mIU/mL)

[figure not shown]
For initially seropositive: antibody concentration at least four times the pre-vaccination antibody concentration

N = number of subjects with both pre- and post-vaccination results available

n(%) = number(percentage) of responders

95% CI = exact 95% confidence interval; LL = lower limit, UL = upper limit

Template 14 Anti-HBs antibody concentrations post challenge as a function of pre-challenge concentrations, with regression line (ATP cohort for analysis of immunogenicity)

Regression equation and R^2 is given by

$$y = (a) + (b)x$$

$$R^2 = (c)$$

Where,

y= post challenge dose (log)

x= pre challenge dose (log)

R^2 = proportion of variation in post challenge dose (log) that is predictable from pre challenge dose (log)

$R^2 = (c)$ may be interpreted as follows: "(c) % of the variation in response variable is explained by regressors or regressors predict response variable by (c) %"

Template 15 Number and percentage of subjects who received study vaccine dose (Total vaccinated cohort)

		HBV Group N = XXX	
Total number of doses received	n	%	
1			

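### Does pooling all subjects with pre-challenge anti-HBs of 10 mIU/ml or more in one response stratum leave a gap in the analysis?

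*SAP*

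**What the plan says.** SAP section 6.3.1 tabulates the post-dose percentages and GMCs "in relation to their pre-challenge dose status (< 6.2 mIU/ml, ≥ 6.2 mIU/ml - < 10 mIU/ml, ≥ 10 mIU/ml) will be tabulated", and uses the same three strata for the anamnestic response. Template 11 ("GMCs for anti-HBs antibody concentrations stratified based on the pre-challenge dose status") and Template 13 ("Anamnestic response for anti-HBs antibodies at one month after the challenge dose stratified based on the pre-challenge dose status") have matching rows, plus an overall or total row.

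Protocol section 10.7 planned the response tables "in relation to their pre-challenge dose status (< 6.2 mIU/ml, < 10 mIU/ml, ≥ 10 mIU/ml) will be tabulated". It used a cut at 100 mIU/ml before the dose only for the persistence percentages: "≥ 10 mIU/ml to < 100 mIU/ml, and ≥ 100 mIU/ml, with exact 95% CI will be calculated". SAP section 9 states that "The analysis to summarize the number and percentage of subjects between >10 mIU/mL and < 100 mIU/mL planned in the protocol was removed". It also narrows the middle response stratum from below 10 to 6.2 to below 10, and leaves the top stratum as it was.

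For subjects seropositive before the dose, SAP section 11.2.4 defines an anamnestic response as at least a "4-fold rise in post-vaccination anti-HBs antibody concentrations in subjects seropositive at the pre-vaccination time point". On interpretation, SAP section 7 says "All analyses are descriptive".

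**The concern.** The value 100 mIU/ml matters in this study. It is the primary threshold after the dose and a secondary endpoint before it. The top response stratum mixes two kinds of subject around that value. Those already at 100 or more meet the primary threshold before they are vaccinated, yet need at least 4 × 100 = 400 mIU/ml to count as anamnestic responders. Those at 10 to below 100 have still to reach 100, and need between 4 × 10 = 40 and just under 400 for a 4-fold rise. The two bands thus face different hurdles, and the differences run in opposite directions on the two endpoints.

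The row may also be the largest one: Protocol section 1.2.1 reports that more than 60% of subjects in the earlier studies were still seroprotected. The SAP's removal of the 10 to below 100 percentage can look like the loss of the one place where the bands were separated. If so, a reader could not tell response to the dose from persisting antibody, and a low anamnestic rate in one band could be hidden in the pooled row.

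**Working it through.** **1. Is the primary result affected?** The inputs are in Protocol section 10.3: 270 evaluable subjects, true rate 95%, lower limit to exceed 90%, one-sided level 0.025. The smallest count r with P(X ≥ r | 270, 0.90) ≤ 0.025 is r = 253 (tail probability 0.0218; r = 252 gives 0.0368). This is also the smallest count whose exact lower limit exceeds 90% (253/270: 90.1%; 252/270: 89.7%). Power is P(X ≥ 253 | 270, 0.95) = 86.7%, against the stated 86% or more. Pre-dose strata do not enter this calculation.

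**2. Did the SAP drop a planned response stratum?** No. Side by side, the response strata are:

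| Document | Lower strata (mIU/ml) | Top stratum |
|---|---|---|
| Protocol 10.7 | <6.2; <10 | ≥10 |
| SAP 6.3.1, Templates 11 and 13 | <6.2; ≥6.2 to <10 | ≥10 |

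The removed 10 to below 100 item was a pre-dose percentage, never a response stratum. Its count still follows from the pre-dose row of Template 9: n(≥10) − n(≥100).

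**3. Are the strata arbitrary?** No. Protocol section 10.5 and SAP section 11.2.4 define status at two points: 6.2 mIU/ml (seropositive) and 10 mIU/ml (seroprotected). The three strata are the classes these cut-offs form. The anamnestic definition itself separates only seronegative from seropositive subjects. The value 100 serves as a response threshold and a persistence percentage, and is not defined as a pre-dose status.

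**4. Are the stated objectives served?** Persistence: Template 9, pre-dose row. Response at 100 or more, seroprotection and concentrations after the dose: Template 9, post-dose row, and Template 11. Anamnestic response: Templates 12 and 13.

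**5. What can be recovered for subjects below 100 before the dose?** Template 11 has a pre-dose and a post-dose row in each stratum, each with a column for ≥100. Let N be the subjects with both results, k those at ≥100 before the dose and x those at ≥100 after it. If d of the k fall below 100, the number who rise to 100 from below is x − (k − d). So (x − k)/(N − k) is the rate among subjects below 100, exactly if d = 0 and otherwise as a lower bound.

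As an illustration, take x = 254 of N = 270 (94.1%, the rate Protocol section 10.3 gives for the 12-13-year study; exact lower limit 90.6%). Assume k is 10%, 20% or 30% of 270, with d = 0; the documents do not give k.

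| k | (x − k)/(N − k) | Rate | Exact 95% lower limit |
|---|---|---|---|
| 27 | 227/243 | 93.4% | 89.5% |
| 54 | 200/216 | 92.6% | 88.2% |
| 81 | 173/189 | 91.5% | 86.6% |

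These figures would come from the planned table without any new row.

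**6. What about the anamnestic rate and post-dose GMC by band?** The summary templates do not give these. Template 14 does report the equation y = a + bx for log post-dose on log pre-dose concentration, with R². Taking base-10 logs, as in the GMC definition, the predicted post-dose geometric mean at pre-dose level c is 10^(a + b·log10 c), and the predicted fold rise is 10^(a + (b − 1)·log10 c). At c = 10 the rise is 10^(a + b − 1); at c = 100 it is 10^(a + 2(b − 1)). This addresses response against persisting antibody on a continuous scale, though not as an observed rate. For observed values, Protocol section 10.9.1 and SAP section 8.1 both place the individual data in the Clinical Study Report along with the analyses, so the rate and GMC for any band can be calculated from the report.

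**The case for a change.** The strongest case for the split is that pooling can hide a difference, and in a descriptive study the tables are the result. Assume 176 subjects at ≥10 before the dose, 44 of them at ≥100, with anamnestic rates near 98% (129/132) in the lower band and 75% (33/44) in the upper. The pooled row would show (129 + 33)/176 = 162/176 = 92.0% (exact 95% CI 87.0 to 95.6%), and the lower rate would not be visible. Splitting the row needs no new data, and a regression line is no substitute for an observed rate with its interval.

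The arithmetic stands, and so does the reading of the mock tables: none of Templates 9 to 14 gives an observed anamnestic rate or GMC by band. But the 98%, the 75% and the band sizes are all assumed. A lower rate above 100 could also come partly from the 400 mIU/ml hurdle, so it would not by itself show weaker immune memory. The added row might be imprecise: at about 95% responders, 26/27 has an exact 95% CI of 81.0 to 99.9%, and 77/81 has 87.8 to 98.6%. Finally, the full list of tables is in a separate contents list (SAP section 10) that is not among the documents, and Annex 3 describes its displays as illustrative. That no table gives the split is therefore shown only for the SAP text and its mock templates.

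**Conclusion.** The concern does not hold. The SAP keeps the top response stratum that the protocol planned, the strata match the status definitions in both documents, and following the plan as written gives sound results for every stated objective. The primary endpoint, the sample size and the power are unaffected, and no decision rule depends on the strata.

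The remaining point is narrow: the observed anamnestic rate and post-dose GMC for 10 to below 100 and for 100 or more are not set out in the mock summary tables. They can be calculated from the individual data in the study report. Their practical importance is unknown, because the documents give neither the pre-dose share at 100 or more nor an anamnestic rate within the ≥10 stratum. The conclusion rests on the individual data being reported as both documents say. An additional descriptive split would be a matter of preference: it would correct no result and change no conclusion.
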